## 5.2.5 Other safety parameters

### 5.2.5.1 Suicidal risk assessment and reporting

The C-SSRS is an investigator-rated interview, developed by clinical experts in cooperation with the FDA, assessing both suicidal behavior and suicidal ideation. It does not give a global score but provides some categorical and some severity information specifically for behavior and ideation.

The C-SSRS interview may be administered by any type of physician, psychologist, clinical social worker, mental health counselor, nurse, or research coordinator with C-SSRS training. It has a typical duration of five minutes and causes only a low burden on patients. At a minimum, the interview consists of 2 screening questions related to suicidal ideation and 4

related to suicidal behavior and may be expanded to up to 17 items in case of positive responses. In this trial paper forms will be used for the assessment of the C-SSRS.

The C-SSRS has been widely used in large multinational clinical trials. The C-SSRS will be administered at the screening visit (using the “baseline/screening” version) with the aim to exclude subjects with a lifetime history of suicidal ideation and behavior. After the baseline visit, the assessment “since last visit” will be performed at clinic visits as specified in the [Flow Chart](#). The Investigator is to review positive and negative reports for plausibility and clinical relevance. Doubtful reports may be repeated, or reports may be validated by a consulting psychiatrist. If there is a positive report of suicidal behavior or suicidal ideation type 4 or 5 after start of trial, the Investigator is to immediately interview the patient during the clinic visit and advise the patient to consult with a psychiatrist. If the positive report is confirmed, appropriate actions for the patient’s safety must be initiated. Treatment with trial medication should be stopped and patient should be discontinued from the trial. Additionally, all C-SSRS reports of suicidal ideation type 4 or 5 and all reports of suicidal behavior must be reported as separate SAEs by the Investigator. For ‘Self-injurious behavior, no suicidal intent’ (Type 11) standard AE / SAE reporting rules are to be applied. For each negative report (suicidal ideation type 1, 2 or 3) after start of the trial, the Investigator is to decide based on clinical judgment whether it represents an AE as defined in the protocol, and if it is considered an AE then it must be reported accordingly.

#### 5.2.5.2 Self-monitoring of blood glucose

T2DM patients taking antidiabetic medication will be provided with a SMBG device for use at home during the treatment period for self-measurement of blood glucose. Patients may also use their own device for SMBG monitoring. The SMBG device will be dispensed to the patients at randomization (Visit 2). Instructions on the proper use of the SMBG equipment will be provided to the patient by the site staff.

SMBG measurements in a fasted state (fasting for at least 10 hours) should be performed regularly. Recommendations are as follows:

- daily during the treatment period;
- at any time, they experience signs/ symptoms of hypoglycemia.

Refer to [Section 4.2.1](#) for information on handling of hypoglycemic events.

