- Anti-drug antibodies (ADA) and neutralizing antibodies (NAb), peptides as BI 456906 are able to induce antibody development

These side effects, which are known to be dose dependent, can be reduced by careful dose escalation, are easy to monitor, and, therefore, are manageable in clinical trials. In addition, tolerability and safety data is very important in this drug class and plays an essential role in the optimal dose finding. It is also well known that the gastrointestinal disorders are temporary, and most patients adapt to GLP-1R agonist-based compounds during dose escalation and/ or maintenance period.

In this trial the following safety measures will be applied in order to minimize the risk for trial patients:

- An extensive safety laboratory testing will be performed at all site visits.
- Patients with T2DM taking antidiabetic medication will be recommended to measure their fasted blood glucose at home daily and to contact the Investigator for safety related measures.

- If patients develop persistent or recurrent severe hypoglycemic episodes (fasted blood glucose level of 54 mg/dL (3.0 mmol/L) or below) they will be asked to reduce the dose of or discontinue any concomitant antidiabetic medication. Antidiabetic medications are allowed to be interrupted under certain clinical circumstances in order to avoid hypoglycemia. Investigators may decide to keep patients solely on trial treatment if there is evidence of glycemic normalization, which is a well-known effect of glucagon receptor agonists. Hypoglycemic episodes as well as their relationship to the trial treatment will be strictly monitored by investigators and appropriately reported. In patients experiencing hypoglycemia, characteristics of episodes, including frequency and severity, will determine whether hypoglycemia needs to be classified as treatment-related adverse events.
- Patients in the placebo group will remain on standard of care that includes diet and exercise counseling as per local standard, and thorough surveillance.
- There are no risks expected by stopping the trial medication during the course of the trial and no down titration is needed.
- Electrocardiogram (ECG) monitoring will be performed at screening, randomization and at all site visits during the trial, and criteria for heart rate, QT prolongation and cardiac conduction disorders are defined.

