### Hypoglycemic events

T2DM patients should contact the site any time their fasted blood glucose level measured with a SMBG device drops below 70 mg/dL (3.9 mmol/L).

Investigators are asked to assess the frequency of detection of the glucose alert value of 70 mg/dL (3.9 mmol/L) or less and to carefully assess hypoglycemic episodes following the 2017 American Diabetes Association position statement on glycemic targets. Investigators should consider lowering the dose of or to discontinue the concomitant antidiabetic medication and to implement additional glucose monitoring as needed.

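### The patient's numeric rule for calling the site (SMBG below 70 mg/dL) covers fasted values only, so a non-fasted symptomatic low has no numeric contact trigger in the protocol text

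*Protocol*

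**What the plan says.** Three protocol sections bear on this.

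- **Section 5.2.5.2 (Self-monitoring of blood glucose).** T2DM patients on antidiabetic medication receive a home meter. The lead sentence is "SMBG measurements in a fasted state (fasting for at least 10 hours) should be performed regularly". Two bullets follow: a daily reading during treatment, and a reading "at any time, they experience signs/ symptoms of hypoglycemia". The section sets no threshold of its own and points to Section 4.2.1 "for information on handling of hypoglycemic events".
- **Section 4.2.1 (Hypoglycemic events).** Patients with T2DM "should contact the site any time their fasted blood glucose level measured with a SMBG device drops below 70 mg/dL". The next paragraph addresses investigators. They are to "assess the frequency of detection of the glucose alert value of 70 mg/dL (3.9 mmol/L) or less", to evaluate episodes, and to consider lowering or stopping antidiabetic drugs and adding glucose monitoring. Nothing in that paragraph depends on fasting.
- **Section 1.4.2 (Risks).** Patients are advised to measure fasted glucose daily and "to contact the Investigator for safety related measures"; no number is given. Severe episodes are described by a "fasted blood glucose level of 54 mg/dL (3.0 mmol/L) or below". If they persist or recur, antidiabetic medication is to be reduced or stopped. The section also says "Antidiabetic medications are allowed to be interrupted under certain clinical circumstances in order to avoid hypoglycemia" and that investigators will monitor hypoglycaemic episodes strictly. Neither of these two statements carries a fasting condition.

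**The concern.** A patient who follows Section 5.2.5.2, tests because of symptoms two hours after lunch and reads a low value is sent to Section 4.2.1 for what to do. The contact rule there, as worded, does not cover that reading. The investigator's rule in the next paragraph does cover it, but only once the site knows of it. So the rule that prompts the patient to report is narrower than the rule on which the investigator acts, and the protocol gives no reason for the difference.

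What is at stake is patient safety, not inference. Section 1.4.2 counts low blood glucose in patients with diabetes among the expected side effects of the class. Global Amendment 1 records that the SMBG and hypoglycaemia guidance in Sections 4.2.1 and 5.2.5.2 was added because a health authority asked for monitoring and mitigation in patients prone to hypoglycaemia. If a non-fasted low is not reported promptly, review of the patient's antidiabetic drugs may come later than it could.

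**Working it through.** No arithmetic decides this point; it turns on the scope of each glucose threshold. The protocol contains three.

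| Place | Threshold | Limited to fasted values? | Who acts, and how |
|---|---|---|---|
| Section 4.2.1, contact rule | below 70 mg/dL | yes | patient contacts site |
| Section 4.2.1, alert value | 70 mg/dL or less | no | investigator assesses frequency and episodes |
| Section 1.4.2, severe episodes | 54 mg/dL or below | yes | antidiabetic medication reduced or stopped |

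1. Numeric thresholds addressed to the patient as a reason to call: one. Of these, covering a non-fasted reading: none.
2. Is a non-fasted reading recommended at all? The symptom bullet in Section 5.2.5.2 sits under a sentence asking for a fast of at least 10 hours. Taken literally, a symptomatic patient would have to fast before testing. That cannot be combined with testing at any time, so the bullet must mean a reading without regard to fasting.
3. Where does that reading go? Section 5.2.5.2 refers it to Section 4.2.1, whose contact rule excludes it by the word *fasted*.
4. What else could bring the low to the site's attention?
   - Section 1.4.2 recommends contact with the investigator and gives no cut-off, although the advice follows directly on the daily fasted reading.
   - Section 4.1.4 has the patient answer side-effect questions in the eDiary and gives the investigator immediate access to it. It states no glucose threshold.
   - The Flow Chart reviews adverse events at every visit and the patient diary at every visit from Week 1. Visits are weekly through Week 24 (for example Day 162 to Day 169, 169 − 162 = 7 days). In maintenance they are four weeks apart (Day 169 to Day 197, 197 − 169 = 28 days).
5. These routes narrow the gap, most clearly during dose escalation. None of them gives the patient a number for a non-fasted reading.
6. The 54 mg/dL parenthesis is a consistency point only. It does not stop an investigator from acting on a non-fasted low, because the rest of Section 1.4.2 and the investigator paragraph of Section 4.2.1 permit action whatever the fasting state.

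**The case against.** The strongest reply is that the gap needs one lenient and one strict reading. If *fasted* is read strictly in both sections, the protocol recommends no non-fasted test, so there is no uncovered reading. If it is read sensibly in both, the symptomatic reading goes to Section 4.2.1 and is handled there. This has some force, but it does not remove the point. The lenient reading in Section 5.2.5.2 is forced by the text, because testing at any time and a 10-hour fast contradict each other. Nothing forces a reader to ignore *fasted* in Section 4.2.1, where a fasted-only call rule is workable on its face. Even on the objector's readings the wording needs repair: strictly, the symptom bullet is unusable; leniently, *fasted* in the contact rule has no function.

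The second reply is that existing cover is substantial and that patients act on what site staff and patient materials tell them, not on the protocol. This stands. Section 5.2.5.2 has site staff instruct patients on the meter, and the patient materials are not in the file. Confidence therefore attaches to the protocol wording, not to any delay in practice.

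The third reply is that the health authority's request proves little. This also stands: the amendment log shows why guidance was added, not that the authority wanted a non-fasted trigger or found the text wanting.

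**Conclusion.** The point holds as a minor patient-safety wording correction. Section 4.2.1 limits the patient's only numeric contact rule to fasted values, while Section 5.2.5.2 recommends a symptom-triggered reading and sends it to that rule. The size of the consequence cannot be stated: the documents give no frequency of hypoglycaemia and no data on how quickly lows reach the site by other routes. The conclusion assumes that the symptom-triggered reading is meant to be taken without a fast, and it concerns the protocol text only.

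Stronger readings are not supported.

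- A reader might infer that non-fasted lows go unmonitored. The investigator paragraph, the strict monitoring of episodes, eDiary access and adverse event review at visits say otherwise.
- A reader might express the gap as the share of the day that falls outside a 10-hour fast. The documents give no meal times, Section 4.2.1 states no fasting duration, and readings are taken when fasted or when symptoms occur, not at random times. A share of clock time would say nothing about missed lows.
- A reader might take the 28-day maintenance interval as the expected delay. It is only a loose upper bound, since the patient may call or make an eDiary entry sooner.
- A reader might suspect an effect on results. Home glucose readings are not among the safety variables in SAP Section 5.4.1, and the contact rule enters no endpoint or planned analysis.

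**What to change.** - **Section 4.2.1:** delete *fasted* from the contact rule, so that any SMBG value below 70 mg/dL prompts a call.
- **Section 5.2.5.2:** separate the daily fasted reading from the symptom-triggered reading, and state that the latter needs no fast.
- **Section 1.4.2 (optional, for consistency):** delete *fasted* from the 54 mg/dL parenthesis.
- Check that the patient instructions carry the same wording.

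The thresholds and the investigator's actions stay as they are, and no device or visit is added. The cost is one deleted word, one split list and one optional deletion. The downside is some additional site contacts.

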### 5.2.6 Assessment of adverse events

#### 5.2.6.1 Definitions of AEs

##### 5.2.6.1.1 Adverse event

An AE is defined as any untoward medical occurrence in a patient or clinical investigation subject administered a medicinal product and which does not necessarily have to have a causal relationship with this treatment.

An AE can therefore be any unfavourable and unintended sign (including an abnormal laboratory finding), symptom, or disease temporally associated with the use of a medicinal product, whether or not considered related to the medicinal product.

The following should also be recorded as an AE in the eCRF and BI SAE form (if applicable):

- Worsening of the underlying disease or of other pre-existing conditions,
- Changes in vital signs, ECG, physical examination and laboratory test results, if they are judged clinically relevant by the Investigator.

If such abnormalities already exist prior to trial inclusion, they will be considered as baseline conditions and should be collected in the eCRF only.

#### 5.2.6.1.2 Serious adverse event

A serious adverse event (SAE) is defined as any AE, which fulfils at least one of the following criteria:

- results in death,
- is life-threatening, which refers to an event in which the patient was at risk of death at the time of the event; it does not refer to an event that hypothetically might have caused death if more severe,
- requires inpatient hospitalisation or prolongation of existing hospitalisation,
- results in persistent or significant disability or incapacity,
- is a congenital anomaly / birth defect,
- is deemed serious for any other reason if it is an important medical event when based on appropriate medical judgement which may jeopardise the patient and may require medical or surgical intervention to prevent one of the other outcomes listed in the above definitions. Examples of such events are intensive treatment in an emergency room or at home for allergic bronchospasm, blood dyscrasias or convulsions that do not result in hospitalisation or development of dependency or abuse.

For Japan only: the following events will be handled as “deemed serious for any other reason”. AEs which possibly lead to disability will be reported as SAEs.

#### 5.2.6.1.3 AEs considered “Always Serious”

In accordance with the European Medicines Agency initiative on Important Medical Events, Boehringer Ingelheim has set up a list of AEs, which by their nature, can always be considered to be “serious” even though they may not have met the criteria of an SAE as defined above.

The latest list of “Always Serious AEs” can be found in the eDC system. A copy of the latest list of “Always Serious AEs” will be provided upon request. These events should always be reported as SAEs as described in [Section 5.2.6.2](#).

Cancers of new histology and exacerbations of existing cancer must be classified as a serious event regardless of the time since discontinuation of the trial medication and must be reported

as described in [Section 5.2.6.2](#), subsections “AE Collection” and “AE reporting to Sponsor and timelines”.

#### 5.2.6.1.4 Adverse events of special interest

The term adverse events of special interest (AESI) relates to any specific AE that has been identified at the project level as being of particular concern for prospective safety monitoring and safety assessment within this trial, e.g., the potential for AEs based on knowledge from other compounds in the same class. AESIs need to be reported to the Sponsor’s Pharmacovigilance Department within the same timeframe that applies to SAEs, please see [Section 5.2.6.2.2](#).

Hepatic injury is considered as AESI. It is defined by the following alterations of hepatic laboratory parameters as defined by the removal and stopping criteria in [Section 3.3.4.1](#). and [Section 10.1](#).

These laboratory findings constitute a hepatic injury alert and the patients showing these laboratory abnormalities need to be followed up according to the “DILI checklist” provided in the ISF.

In case of clinical symptoms of hepatic injury (icterus, unexplained encephalopathy, unexplained coagulopathy, right upper quadrant abdominal pain, etc.) without laboratory results (ALT, AST, total bilirubin) available, the Investigator should make sure these parameters are analysed, if necessary, in an unscheduled blood test. Should the results meet the criteria of hepatic injury alert, the procedures described in the DILI checklist should be followed.

#### 5.2.6.1.5 Adverse events requiring adjudication

Pre-specified AEs critical for the assessment of safety of BI 456906 will be centrally adjudicated in a blinded fashion by an independent external Clinical Event Committee (CEC).

Definitions of the adjudicated events and the principles of standardised data collection in the centralised CEC adjudication process are outlined in the separate CEC Charter. For further details refer to [Section 8.7](#).

#### AEs requiring adjudication

- All-cause death
- Cardiovascular event
- Cerebrovascular disease
- Heart failure requiring hospitalisation
- Pancreatitis
- Neoplasm
- Thyroid mass requiring surgery

#### 5.2.6.1.6 Intensity (severity) of AEs

The intensity (severity) of adverse events should be classified and recorded in the eCRF according to the Common Terminology Criteria for Adverse Events (CTCAE) Version 5.0 released on 27 November 2017 [[R18-1357](#)].

#### 5.2.6.1.7 Causal relationship of AEs

Medical judgement should be used to determine whether there is a reasonable possibility of a causal relationship between the adverse event and the given trial treatment, considering all relevant factors, including pattern of reaction, temporal relationship, de-challenge or re-challenge, confounding factors such as concomitant medication, concomitant diseases and relevant history.

Arguments that may suggest that there is a reasonable possibility of a causal relationship could be:

- The event is consistent with the known pharmacology of the drug.
- The event is known to be caused by or attributed to the drug class.
- A plausible time to onset of the event relative to the time of drug exposure.
- Evidence that the event is reproducible when the drug is re-introduced.
- No medically sound alternative aetiologies that could explain the event (e.g., pre-existing or concomitant diseases, or co-medications).
- The event is typically drug-related and infrequent in the general population not exposed to drugs (e.g., Stevens-Johnson syndrome).
- An indication of dose-response (i.e., greater effect size if the dose is increased, smaller effect size if dose is reduced).

Arguments that may suggest that there is no reasonable possibility of a causal relationship could be:

- No plausible time to onset of the event relative to the time of drug exposure is evident (e.g., pre-treatment cases, diagnosis of cancer or chronic disease within days / weeks of drug administration; an allergic reaction weeks after discontinuation of the drug concerned).
- Continuation of the event despite the withdrawal of the medication, taking into account the pharmacological properties of the compound (e.g., after 5 half-lives).  
Of note, this criterion may not be applicable to events whose time course is prolonged despite removing the original trigger.
- Additional arguments amongst those stated before, like alternative explanation (e.g., situations where other drugs or underlying diseases appear to provide a more likely explanation for the observed event than the drug concerned).
- Disappearance of the event even though the trial drug treatment continues or remains unchanged.

#### 5.2.6.2 Adverse event collection and reporting

##### 5.2.6.2.1 AE Collection

The Investigator shall maintain and keep detailed records of all AEs in the patient files.

The following must be collected and documented on the appropriate eCRF(s) by the Investigator:

- From signing the informed consent onwards until the individual patient's end of trial: all AEs (serious and non-serious) and all AESIs.
- After the individual patient's end of trial: the Investigator does not need to actively monitor the patient for new AEs but should only report any cancers of new histology and exacerbations of existing cancer, trial treatment related SAEs and trial treatment related AESIs of which the Investigator may become aware of by any means of communication, e.g., phone call. Those AEs should be reported on the BI SAE form (see Section 5.2.6.2.2), but not on the eCRF.

#### 5.2.6.2.2 AE reporting to the Sponsor and timelines

The Investigator must report SAEs, AESIs, and non-serious AEs which are relevant for the reported SAE or AESI, on the BI SAE form immediately (within 24 hours) to the Sponsor's unique entry point (country specific reporting process will be provided in the ISF). The same timeline applies if follow-up information becomes available. In specific occasions, the Investigator could inform the Sponsor upfront via telephone. This does not replace the requirement to complete and send the BI SAE form.

With receipt of any further information to these events, a follow-up SAE form has to be provided. For follow-up information the same rules and timeline apply as for initial information. All (S)AEs, including those persisting after individual patient's end of trial must be followed up until they have resolved, have been assessed as "chronic" or "stable", or no further information can be obtained.

